# **Study Design**

The overall objective is to determine the extent to which racially congruent Facebook food ads influence adolescents' food purchases and actual caloric intake. We will accomplish these objectives by conducting three randomized controlled trials (RCTs). The first two aims trials will involve 15minute online surveys in which participants (Black and White adolescents) will rate ads then complete a "food purchasing" task through a virtual vending machine. The third trial will involve an in-person, hour long lab study where participants will be shown ads while investigators covertly monitor their eye movements. The first RCT will answer the research question "Does exposure to racially congruent vs. incongruent Facebook ads for unhealthy foods cause Black (vs. White) adolescents to purchase snacks with more calories?". The second RCT will answer: "Does exposure to many "likes" (vs. few "likes") on Facebook ads for unhealthy foods lead to even higher calorie purchases for both Black and White adolescents?". Lastly, the hour-long study will answer the question: "To what extent does the visual attention to foods vs. people vs. "likes" in ads predict adolescents' caloric intake?" (Aim 3). For the first two online survey trials, we will measure the average calories purchased for a snack and for the last trial we will measure the average calories consumed.

<sup>19 Harris JL, Schwartz MB, LoDolce M, et al. Sugary drink FACTS 2014: Some progress but much room for improvement in marketing to youth. *Rudd Center for Food Policy and Obesity: New Haven, CT*. 2014.

<sup>20 Harris JL, Schwartz MB, Munsell CR, et al. Fast food FACTS 2013: Measuring progress in nutrition and marketing to children and teens. *Yale Rudd Center for Food Policy and Obesity*. 2013.

<sup>21 Grier SA, Kumanyika S. Targeted marketing and public health. Annu Rev Public Health. 2010;31:349-369.

<sup>22 Harris JL, Shehan C, Gross R, et al. *Food Advertising Targeted to Hispanic and Black Youth: Contributing to Health Disparities*. Rudd Center for Food Policy & Obesity; 2015.

<sup>23 Story M, French S. Food Advertising and Marketing Directed at Children and Adolescents in the US. *Int J Behav Nutr Phys Act*. 2004;1(1):3.

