# **Methods & Procedure**

**Aim 1:** After obtaining parental permission and assents, participants will view and rate 18 ads in the online survey. They will view and rate one ad before viewing and rating the next ad. They will then complete the food purchasing task. In this task, six foods and six beverages from the brands that target adolescents the most will appear in a virtual vending machine embedded in the online survey. Half of the food items will be healthy snacks and half will be unhealthy, as scored by the Nutrient Profile Model, a validated nutrition rating tool designed by nutritionists and used in public health studies. Three of the beverages will be sugar-sweetened beverages and three will be the zero-calorie versions of those sugar-sweetened beverages. Participants will select one food item and one beverage they would like to consume. To incentivize actual purchasing behavior, we will tell them we will provide \$8 for their snack purchases and they can keep any money they choose not to spend. We will also tell them that we will mail the items to their home. This approach will incentivize adolescents to consider the trade-offs of keeping money vs. spending it on snacks, which is more representative of real-world purchasing behavior. In reality, we will provide the \$8 at the end of the study instead of mailing the items. After the food purchasing task, participants will complete demographic questions and then receive \$25 for participating and \$8 for their snack purchases

**Aim 2:** Parental consent and adolescent assent process will be obtained as described for Aim 1. After providing assent, participants will be randomized to view and rate 18 racially congruent Facebook food ads that feature many (>10,000) or few (<100) "likes." After viewing each ad, they will complete the ad rating questions for that ad (Table 2) before proceeding to the next ad. Participants will then complete the same food purchasing task described in Aim 1(section E.3.4.). Finally, they will complete the demographic questions. At the end of the study, they will view a debriefing statement similar to the statement from Aim 1 (sectionE.3.4). Dynata will then provide each participant with \$25 compensation and \$8 for the purchased snack products.

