Analysis of primary outcome: Linear regression will be used to evaluate whether the number of calories purchased by the adolescents who viewed racially congruent ads differs from those who viewed racially incongruent ads. If the calorie count data are skewed, a suitable transformation (e.g., log) will be applied to improve the approximation of normality. To evaluate our hypothesis that Black adolescents—compared to White adolescents—will purchase more calories after viewing racially congruent ads, an additional model will also include a term for participant race, as well as an interaction term between participant race and ad congruence to determine if there is a differential association. We will also run all models controlling for eating restraint and presence of eating disorders symptoms to examine if those factors affect the number of calories purchased by adolescents. Analyses of secondary outcomes: We will use linear regression models that include participant race, racial congruence, and the interaction of the two as predictors; emotional responses to the ads and time spent viewing ads will be our outcomes. To investigate affective responses to the ad as a potential mediator for the relationship between the type of ad viewed and calories purchased, an additional model will include participant race, racial congruence of the ads, and an interaction term, as well as affective responses to the ads as predictors of calories purchased. We Will assess whether associations between calories purchased and the racial congruence term and the interaction between racial congruence and participant race term are weakened by the addition of affective response to the model. We will use the Bonferroni-holm procedure to correct for multiple comparison

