sample size provides 80% power to detect an effect size of 0.2 SD between conditions. Analytic plans: Descriptive analyses: Data will be summarized as described in Aim 1. We will assess balance by randomization status with respect to demographic and behavioral factors. Adjustment of primary analyses will be undertaken to accommodate any imbalances. Primary outcome: Linear regression will be used to evaluate differences in the mean calories purchased between conditions, with appropriate transformations to improve the approximation of normality if necessary. To explore whether the effect of many vs. few "likes" varies by race, we will include participant race as a main effect, as well as an interaction term between race and condition. We will also use linear regression to adjust for demographic and behavioral characteristics to investigate how these factors relate to responsiveness to ads. We will also conduct sensitivity analyses to control for the presence of eating disorder symptoms measured at the end of the study. Finally, participants who fail our data integrity check questions will be excluded. This is expected to be <9% of participants based on our pilot studies. Secondary outcomes: We will use linear regression models to assess the relationships between the number of "likes" on the ad and cognitive and emotional responses as well as time spent viewing ads. We will evaluate whether the association between the number of "likes" and calories consumed is moderated by affective responses to the model. The Bonferroni-Holm procedure will be used to correct for multiple comparisons.

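### Secondary mechanism analyses: Aim 1 infers mediation from coefficients that shrink by chance in about half of trials, and Aim 2 tests moderation by a response that the exposure may itself change

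*Combined protocol and SAP*

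**What the plan says.** All references are to the combined protocol and SAP.

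**Aim 1 (Data Analysis, analyses of secondary outcomes).** Linear models use race, congruence and their interaction as predictors, and "emotional responses to the ads and time spent viewing ads will be our outcomes". A further model is planned: "To investigate affective responses to the ad as a potential mediator for the relationship between the type of ad viewed and calories purchased". It adds affective response to race, congruence and their interaction as predictors of calories purchased. The team will then assess whether the congruence term and the interaction term are weakened. Nothing says how much weakening counts or how uncertainty enters. Bonferroni-Holm is named for multiple comparisons.

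**Aim 2 (Data Analysis, primary and secondary outcomes).** For the primary outcome, "Linear regression will be used to evaluate differences in the mean calories purchased between conditions". The secondary models relate the number of likes to "cognitive and emotional responses as well as time spent viewing ads". The next sentence asks whether the association between likes and "calories consumed is moderated by affective responses to the model".

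**Order of events (Methods & Procedure, Aim 2).** Participants are randomised to many or few likes. "After viewing each ad, they will complete the ad rating questions for that ad", and "Participants will then complete the same food purchasing task" as in Aim 1.

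**Outcome (Study Design).** "For the first two online survey trials, we will measure the average calories purchased for a snack". Calories consumed belong to the third trial.

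**The concern.** The two aims use the same kind of variable in the same place, between exposure and purchase, but give it different roles and neither role a usable criterion.

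In Aim 1, a coefficient that gets smaller when a covariate is added is not in itself evidence of mediation. Sampling error moves it up or down whether or not affect matters. Without a stated rule, the judgement is made after the data are seen.

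In Aim 2, moderation asks whether the effect of likes differs between participants with stronger and weaker affective responses. Mediation asks whether likes change affect and affect changes purchases. If the second question is meant, as Aim 1 suggests, the wrong test is written down, and a null interaction could be misread as affect playing no part. If the first is meant, the plan does not say why it departs from Aim 1, or how a moderator that the exposure may have changed is to be interpreted.

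What is at stake is the mechanism statement in the report, not the randomised comparison of calories purchased.

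**Working it through.** **1. Outcome and role of affect, by reading.** Study Design, Methods & Procedure and the Aim 2 primary-outcome sentence all give calories purchased for Aim 2. No intake is measured there, so consumed can only mean purchased. Ads are rated after exposure and before purchase. The Aim 2 text models emotional response as an outcome of likes, and Aim 1 names affective response as a potential mediator. I take emotional and affective response to be the same construct, collected in the ad ratings.

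**2. The plan's figures.** SD 400, two-sided alpha 0.017, power 80%, exclusions 9% (Aim 2 says under 9%; 9% used).
- Aim 1: 288 × 0.91 = 262 per race-by-congruence cell, so 524 per ad condition. 400 × (2.387 + 0.842) × √(2/524) = 79.8 calories (plan: 80).
- Aim 2: 600 × 0.91 = 546 per arm. 400 × (2.387 + 0.842) × √(2/546) = 78.2 calories (plan: 78).

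These figures reproduce and are not in dispute. They set the scale below.

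**3. What weakening measures.** With least squares on the same participants,

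coefficient without affect − coefficient with affect = b̂ × (the same coefficient in the model for affect),

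where b̂ is the estimated effect of affect on calories. This holds for both the congruence and the interaction term. Write a for the effect of the ads on affect and b for the effect of affect on calories, both in SD units. With no mediation, a or b is zero, and its estimate is about as likely to be positive as negative. The drop is therefore positive about half the time.

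**4. Aim 1 simulation, no mediation.** 4,000 trials per row, 262 per cell, total effect 80 calories in both races, White as reference. The values of a and b are assumptions.

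| a, b | Congruence smaller | Interaction smaller | Congruence down by over 10% |
|---|---|---|---|
| 0, 0 | 51.1% | 50.1% | 0.6% |
| 0, 0.2 | 50.9% | 52.8% | 13.6% |
| 0, 0.4 | 50.8% | 56.9% | 27.0% |
| 0.2, 0 | 50.3% | 49.8% | 2.9% |
| 0.4, 0 | 52.0% | 49.4% | 8.4% |

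Hand check of the 27.0%: the drop has SD 0.4 × 400 × √(2/262) = 13.98 calories, and 10% of 80 is 8. The upper tail beyond 8/13.98 = 0.57 is about 0.28. A bare percentage threshold would therefore not be a safe rule either, because its error depends on the unknown paths.

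**5. Indirect effect with a 98.3% bootstrap interval** (100% − 1.7%; 1,000 trials, 1,000 resamples).
- Aim 1, no mediation, at (0, 0), (0, 0.2), (0, 0.4) and (0.2, 0): the pooled interval excludes zero in 0.1–2.4% of trials. At least one of the White, Black and between-race-difference intervals does so in 0.1–4.5%.
- Aim 1, true mediation of 0.2 × 0.2 × 400 = 16 calories: detected in 81% pooled and 47–49% within each race.
- Aim 2, no mediation: 0–2.1%. True mediation of 16 or 0.3 × 0.3 × 400 = 36 calories: 82% and 99.5%.

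**6. Moderation is a different question.** In Aim 2, with pure effect modification of 0.2 SD per SD of affect and no mediation, the interaction test (p < 0.017) is positive in 82% of trials and the indirect-effect interval in 2.2%. Each analysis responds to its own question and not to the other.

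**7. Limit of the interval.** With no mediation (a = 0.2, b = 0) but an unmeasured cause loading 0.1, 0.2 or 0.3 on both affect and calories, the interval excludes zero in 1.9%, 9.5% and 54% of trials (Aim 1, pooled) and 1.7%, 12% and 60% (Aim 2).

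**The case against.** Four points deserve weight.

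- **Most of the output is already planned.** Aim 1 regresses emotional response on congruence and puts affective response into the calorie model. Requiring both paths to be significant at 0.017 would falsely indicate mediation in 0–1.8% of no-mediation trials and detect the 16-calorie effect in 79%, much like the bootstrap. This stands, and it keeps the fix cheap. But the plan does not say that the paths will be read that way. It says weakened.
- **Moderation may be intended.** Then an interaction test suits its question. A reader might take an interaction test that is rarely significant under pure mediation as a sign of a poor test. That would be wrong: data with no interaction must give rejections near the nominal rate. The only valid point is that the test does not address whether affect carries the effect.
- **A reader might infer that Aim 1 requires both coefficients to shrink, and so often misses true mediation.** The plan states no such rule. Any miss rate also follows the assumed scenario: both shrink in 51–52% of trials when effect and mediation are equal in both races, and in 65–70% when both are larger in Black participants.
- **The interval does not secure a causal reading.** Correct, as step 7 shows. That calls for a sensitivity analysis and an exploratory label; it does not rescue the weakened criterion, which is exposed to the same confounding.

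**Conclusion.** The concern holds for the secondary mechanism analyses. In Aim 1, weakening as the sole criterion is met for each coefficient in 49–57% of trials with no mediation. The half-chance result follows from the algebra in step 3; the exact range rests on the assumed paths, equal 80-calorie effects in both races, and 9% exclusions. In Aim 2, the sentence as written tests moderation by a variable measured after exposure, without saying why its role differs from Aim 1.

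Two stronger readings are not supported. Consumed does not show that Aim 2 rests on an unmeasured outcome: the surrounding text makes clear that purchased is meant. Nor do the primary analyses suffer: the randomised comparisons, their sample sizes and their detectable differences are untouched. This should be corrected before analysis, but it does not threaten the trials' main results.

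**What to change.** **Aim 1.** Replace the weakened criterion with: *We will estimate the indirect effect of racially congruent vs incongruent ads on calories purchased through affective response, pooled over race as the main estimate, and also by participant race and as the difference between races, each with a 98.3% bootstrap confidence interval. We will report evidence of mediation only if the interval excludes zero.*

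**Aim 2.** Change consumed to purchased, and replace the moderation sentence with the same estimate, 98.3% interval and reporting rule for many vs few likes. If effect modification by affect is really intended, say so and report it separately as descriptive.

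**Both aims.**
- Use the outcome scale of the primary model, including any log transformation.
- Adjust for collected covariates that the ads cannot have changed, such as age and sex.
- State the assumption of no unmeasured confounding between affect and purchases, and add a sensitivity analysis, for example over a range of residual correlations.
- Label the results exploratory and outside the Bonferroni-Holm family.

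**Cost.** A few sentences of wording, plus a bootstrap and a sensitivity analysis on data already being collected. Race-specific intervals have less power (47–49% against 81% pooled for 16 calories), which is why the pooled estimate leads. The answer may be inconclusive, because no interval removes confounding between affect and purchases.

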**Aim 3:** Participants will visit our collaborator [name] in her lab —located at NYU Washington Square Campus—and sit in front of a Tobii eye-tracking computer. The computer monitor displays an advertisement and youth view it as they would any other type of document on a computer. Eye-tracking technology allows for the documentation of fixations, an objective measure of attention, which occurs when an individual pauses to examine or interpret a component of an advertisement or image. The Tobii eye tracking device allows moderately free head movements. It returns a real-time estimate of the left and right eye gaze positions on the screen, as well as the 3D position of the two eyes with respect to the screen center. After obtaining consent and assent in-person, we will ask

participants to "answer a few questions about how they are feeling today" and hunger will be one of the items they rate, which will allow us to unobtrusively measure baseline hunger and control for it during analyses. We will then tell them that we will show them a series of images that are for their viewing pleasure, and that we have snacks and a drink they can enjoy as a thank you for participating. Participants will view 30 ads per block that appear at a predetermined rate to hold total viewing time constant across all ads. Researchers will calibrate the eye-tracking computer using a guise developed by our collaborator [name] that asks the participant to count the number of times a ball bounces on the screen (n = 6), "so you can take a moment to let your mind rest after rushing through the busy city to arrive at the lab today." [name] has used this technique on >1,000 participants and <1% noted suspicion.

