During the eye-tracking task, snacks will be positioned in bowls on a Cardinal Detecto stainless steel scale that looks like a serving tray but transmits weight information wirelessly to the control room. Similar to previous food ad studies,we will include two unhealthy snacks and two healthy snacks with a 20-ounce bottle of water. The unhealthy snacks will include M&Mcandies (high-fat, sweet) and Doritos chips (high-fat, savory). The healthy snacks will include Quaker Rice Cakes (lowfat, savory) and grapes (low-fat, sweet). To minimize the risk of ceiling effects (i.e., where participants eat all the food), we will include 150g of each snack: M&Ms (296-ml bowl), Doritos and Quaker Rice Cakes (1,419-ml bowls), and grapes (473-ml bowl). Our pilot data also suggest—and a systematic review reinforces—that most participants eat during food ad studies. To conclude the study, participants will complete demographic questions (Table 1). We will use a funneled debriefing procedure to ask participants what they believed was the purpose of the study so we can test for moderation of effects as a function of awareness during analyses. We will disclose the purpose of the study, solicit questions, conduct a second assent procedure after disclosing eye-tracking was used and was ethically approved, and provide the same information from the debriefing form in Aim 1 and 2 (section E.3.4). Finally, we will distribute \$35 compensation in cash and subway/bus fare to cover travel costs. Those who travel by other means will also receive the travel fare.

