**Aim 3-** Statistical considerations: Power and sample size: We based our sample size on the expectation of a racial congruence effect that is small in size for White adolescents (0.2) and larger for Black adolescents (0.3). West our final sample size with the requirement of 80% power to detect the smallest correlation coefficient (at least 0.2) within each group (i.e., 200 Black and 200 White adolescents provide adequate power). Analytic plans: We will follow data cleaning procedures for eyetracking data established by our collaborator [name] for handling data loss or calibration issues.The sampling rate—the proportion of time eyes are directed at the screen—must equal 80% or higher. Participants with <20% sampling rate will be eliminated (typically <5% of participants). Sampling Rates can be low because some rare types of cornea refractions and contact lens types impair the reflection of light the system measures. To account for nonindependence in consumption across blocks, we will conduct analyses using the MIXED procedure in SPSS, and calculate degrees of freedom using a Satterthwaite correction to predict consumption as a function of ad type within blocks 1–4 and separately blocks 5–8. We will include the random intercept of participants, the random intercept of block order, and the random slope of block order to account for linear changes in consumption over time. We will use linear regression to predict calorie intake from visual attention to race-relevant ad features, product, and "likes" for Black and White adolescents

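### In Aim 3 participants can eat while their gaze is recorded, so raw dwell time or fixation counts may fall as intake rises, and an 80% on-screen rule could remove heavier eaters

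*Combined protocol and SAP*

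**What the plan says.** **Eating and gaze recording overlap (Methods & Procedure, Aim 3).** "During the eye-tracking task, snacks will be positioned in bowls on a Cardinal Detecto stainless steel scale". The scale "transmits weight information wirelessly to the control room". Participants are told that the images are for their viewing pleasure and that "we have snacks and a drink they can enjoy as a thank you for participating". The protocol expects that "most participants eat during food ad studies". It states no instruction to keep eyes on the screen.

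**Display time is fixed (same section).** Ads "appear at a predetermined rate to hold total viewing time constant across all ads".

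**Attention is not operationally defined.** The eye tracker is described as allowing "documentation of fixations, an objective measure of attention". Data Analysis, Aim 3, refers only to visual attention to race-relevant features, product and 'likes'. Neither place says whether the variable is a count, a duration or a share.

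**Data quality (Data Analysis, Aim 3).** The sampling rate is "the proportion of time eyes are directed at the screen". One sentence requires at least 80%. The next eliminates participants below 20% and expects this to affect fewer than 5%. The reason given for low rates is that "some rare types of cornea refractions and contact lens types impair the reflection of light the system measures". For data loss and calibration problems the plan relies on a collaborator's published cleaning procedures, which it does not reproduce.

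**Analyses (same section).** A mixed model relates consumption to ad type across blocks, and linear regression predicts calorie intake from visual attention. The elimination rule is not limited to either analysis.

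**The concern.** A participant who looks down to choose and pick up food has eyes off the screen. The sampling rate as defined cannot tell this from a tracking fault. Intake is the outcome, so the outcome can act on the analysis in two ways.

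1. **On the predictor.** With fixed display time, each look at the food is time lost from product, person and 'likes'. A raw total then falls as intake rises, whatever the true relation.
2. **On retention.** If participants must reach a high on-screen proportion to be kept, those who eat most are the likeliest to be lost.

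Aim 3 asks whether attention predicts intake and is sized for a correlation of 0.2. A built-in negative component could hide a modest positive association or produce a false negative one. Controlling for baseline hunger, as planned, does not remove it, because the link is mechanical.

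**Working it through.** **1. The plan's own figure.** Aim 3 states 200 adolescents per race group for 80% power at r = 0.2. No alpha is given for Aim 3, so two-sided 0.05 is assumed. By Fisher's z, n = ((1.960 + 0.842)/atanh(0.2))² + 3 = (2.802/0.2027)² + 3 = 194. At n = 200, power is Φ(0.2027 × √197 − 1.960) = 81.2%. The figure reproduces.

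**2. Form of the bias.** Let S be the feature's share of on-screen gaze, F the off-screen share, and E intake in SD units. Raw dwell is D = S(1 − F). If F rises by b per SD of intake, and ρ is the true correlation of S with E, then

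cov(D, E) ≈ (1 − mean F) × SD(S) × ρ − mean(S) × b.

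The documents give none of these inputs except ρ = 0.2. Assume mean F = 0.10, mean S = 0.30 and SD(S) = 0.08. The first term is 0.90 × 0.08 × 0.20 = 0.0144, and the second is 0.30b. They cancel at b = 0.0144/0.30 = 0.048. Under these inputs, about 5 points more off-screen time per SD of intake would wipe out a true 0.20.

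**3. Simulation of that model.** 1,000,000 draws per row; normal intake; residual SD of F 5 points; F not allowed below zero, which softens the effect slightly.

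| b (points per SD of intake) | Observed r, true 0 | Observed r, true 0.20 | Lost under 80% rule: all | Heaviest-eating third | Lightest third |
|---|---|---|---|---|---|
| 0 | 0.00 | 0.20 | 2% | 2% | 2% |
| 3 | -0.12 | 0.08 | 4% | 10% | 0.5% |
| 6 | -0.22 | -0.03 | 10% | 27% | 0.2% |
| 10 | -0.32 | -0.15 | 19% | 52% | 0% |

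The observed r values use raw dwell with no exclusion at 80%. At an observed r of 0.08 and n = 200, power is Φ(0.0802 × √197 − 1.960), about 20%.

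**4. A second model, extended to weak links.** Intake is skewed (gamma, shape 2), product share has mean 0.35 and SD 0.08, and the link is the correlation of off-screen share with intake.

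| Off-screen mean / SD | Link | Observed r, true 0 | Observed r, true 0.20 | Lost under 80% rule: all | Top intake quartile | Bottom quartile |
|---|---|---|---|---|---|---|
| 8% / 5 | 0.1 | -0.02 | 0.17 | 3% | 4% | 2% |
| 8% / 5 | 0.3 | -0.07 | 0.12 | 3% | 5% | 2% |
| 8% / 5 | 0.5 | -0.12 | 0.07 | 3% | 6% | 1% |
| 15% / 10 | 0.5 | -0.23 | -0.07 | 26% | 50% | 12% |
| 15% / 10 | 0.7 | -0.32 | -0.17 | 26% | 64% | 7% |

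**5. The 20% rule.** In every scenario of both models it removes at most 0.02% of participants.

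**6. Share of on-screen gaze.** Before exclusion this measure returns 0.00 and 0.20. After an 80% rule, a true 0.20 becomes 0.16 to 0.20 in the first model, and 0.13 to 0.19 in the second for links of 0.5 to 0.7.

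**The case against.** - **Selection depends on the threshold.** A reader might infer that heavy eaters are lost at any cut-off. The documents do not support this. The only sentence that expressly removes participants uses 20%, and at 20% almost nobody is removed for eating. The selection concern stands only if 80% governs. A 26% loss would also sit badly with the plan's own expectation of under 5%, although that expectation may come from tasks without food.
- **Raw totals are not stated to be the measure.** A reader might infer that eating does lower the planned attention variable. The plan names fixations and visual attention without defining the variable, and the cited cleaning procedures cannot be seen. What stands is that nothing in the text rules out a raw total.
- **The size is assumed.** The documents give no off-screen time, tray position or relation between eating and gaze, and people can eat without looking away. With a weak link and little off-screen time, the loss is small (0.20 becomes 0.17).
- **Recovery by the share measure is partly by construction.** The simulations define the true association on the share scale. If total exposure to a feature drives intake, the share is a different quantity.
- **The ad-type model.** A reader might infer that its contrast is biased. That is not shown: dropping a participant removes all of that person's blocks, so the cost shown is to precision and generalisability.

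**Conclusion.** The point holds as a gap in definition with a predictable direction. Concurrent eating, fixed display time and a quality metric based on on-screen time together let intake lower any raw dwell or count measure, which biases the attention-intake association downward. That part depends on no threshold, so reconciling 80% with 20% does not settle it. The selection part does depend on the threshold: potentially large at 80%, negligible at 20%.

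Confidence is high for the structure and low for the size. Across the assumed weak to strong links, a true 0.20 appears as about 0.17 to -0.17 with raw dwell. This is worth correcting because it bears on Aim 3's main question and costs little to guard against.

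**What to change.** 1. **Define attention** to product, person and 'likes' as each feature's share of valid on-screen gaze time. Keep raw dwell as a sensitivity analysis, since it addresses total exposure.
2. **Reconcile the 80% and 20% sentences**, and state that the gaze exclusion applies only to the attention analyses. Keep every participant with intake data in the mixed model of consumption by ad type, which needs no gaze data.
3. **Report retention by intake** and repeat the attention analysis without the exclusion. Where the recorded data allow, separate looks away from signal loss. The protocol says that weights are transmitted, but not that they are time-stamped or synchronised with gaze, so the plan should not depend on that.

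The cost is revised wording and some recoding, with no extra participants or visits. The downside is that shares are noisier for participants who look away a lot, and they measure relative rather than total exposure. Weighting by valid gaze time can ease the first; the raw-dwell sensitivity analysis covers the second.
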